Pneumonia	Identified using appropriate ICD codes. Coded as binary (yes/no) variables	PSM
Acute bronchitis	Identified using appropriate ICD codes. Coded as binary (yes/no) variables	PSM
Dyspnea	Identified using appropriate ICD codes. Coded as binary (yes/no) variables	PSM
Alcohol dependence	Identified using appropriate ICD codes. Coded as binary (yes/no) variables	PSM
Smoking dependence	Identified using appropriate ICD codes. Coded as binary (yes/no) variables	PSM

Using propensity score matching (PSM) technique, we will develop matched cohorts of patients between the ICS+Tio and ICS/LABA groups. We will conduct 1:2 matching using nearest neighbor matching approach. Upon completion of matching, we will assess whether the cohorts are balanced by examining the statistically significant differences at $p < 0.05$. We will also assess balance by calculating standardized mean differences (SMD). An SMD < 0.1 will be considered balanced. Follow-up time will be calculated between index date and 'Censor date' which will be defined as the date of either one of the following events: 1. Date of first exacerbation, 2. Date of medication switch, 3. Discontinuation of medication (defined as date of prescription claim plus days' supply, plus 50% additional days), 4. Enrollment end date, or 5. Last date available in the dataset/End of study period. In this "new user", study design, primary analysis will be an "as-treated" analysis. In order to attribute events and outcomes to patients during the time that they are exposed to treatment (based on days-supply of prescription claims + a buffer window) as well as account for differences in inter-group adherence levels, we will use a time-varying covariate approach to classify drug exposure time for each comparator drug during follow up. This approach has been chosen to minimize bias based on potentially large differences in medication adherence rates, by only attributing outcomes to the time in which patients have medication in their possession based on days' supply as described below. For each individual study drug, we will identify and define medication exposure and non-exposure windows during the follow-up time for each medication using the date of prescription filled plus the days' supply listed on the prescription claim plus 50% additional days (to account for residual doses in canister, poor real-world adherence and latency of drug effects). For example, exposure start and stop dates

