9.3.2.2 Secondary endpoints

Secondary endpoints will include:

- Time to first moderate-or-severe exacerbation
 - Any systemic corticosteroid use or
 - A hospitalization with a primary diagnosis of asthma or
 - An ER visit with a primary diagnosis of asthma
- Proportion of patients with exacerbation
- Rate of exacerbation at 6 months and one year
- Proportions of patients with Health care resource utilization (HCRU). HCRU is defined as hospitalizations, emergency room (ER) visits, and outpatient visits during follow-up, all-cause and asthma related.
- Mean monthly HCRU (including frequency of hospitalizations, ER visits, OP visits)
- Proportion of patients with use of rescue medications (defined as patients with one or more SABA claims during the follow-up period)

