9.7 DATA ANALYSIS

9.7.1 Main analysis

Sample attrition at each step of the inclusion-exclusion criteria will be provided. We will develop the breakdown of the distribution of demographic, comorbidity, and baseline measures prior to and after the PSM (unmatched and matched cohorts). Significance of differences will be tested at $P<0.05$ for the matched cohort. Additionally, we will consider the use of standardized mean differences as noted above, in which $SMD <0.1$ indicates balance of baseline covariates. The primary endpoint measure is time to first severe exacerbation and severe exacerbation will be defined as a hospitalization or an ER visit with a primary diagnosis of asthma. We will calculate the time in days to first exacerbation. Also, as part of the primary end point analysis, we will develop KM curves based on initial exposure and conduct time varying Cox proportional hazards modeling accounting for changes in exposure status over the follow up time to estimate the risk of exacerbation between ICS+Tio vs. ICS/LABA. Secondary endpoints will include a number of measures. We will calculate the time in days to first moderate-or-severe exacerbation defined as use of systemic corticosteroid or a hospitalization or ER visit with a primary diagnosis of asthma. KM curves based on initial exposure and time varying Cox PH models will be conducted for this secondary end point as well. We will also calculate and compare the rate of exacerbation, proportion of patients with exacerbations after 6 months and one year among the sub-population of patients having at least 6 months and a year of follow-up, respectively. We will report rates in patient-years to account for variable follow-up time. We will also compare the mean monthly (to account for variable follow-up time) per patient HCRU (all-cause and asthma related hospitalizations, ER visits, and outpatient visits) during the follow-up period, between the two groups. Proportions of patients with and without rescue medication use will be compared between the two groups as well.

Proprietary confidential information © 2021 Boehringer Ingelheim International GmbH or one or more of its affiliated companies

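### The only follow-up definition ends at the first exacerbation, so HCRU, the exacerbation rate and the 6- and 12-month measures lose repeat events and later care

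*Combined protocol and SAP*

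**What the plan says.** Section 9.1 defines follow-up once: "Follow-up time will be calculated between index date and 'Censor date' which will be defined as the date of either one" of five events. The list opens with "1. Date of first exacerbation, 2. Date of medication switch" and goes on to "3. Discontinuation of medication (defined as date of prescription claim plus days' supply, plus 50% additional days"), end of enrollment, and end of data. It is not restricted to particular endpoints, and it does not say whether the exacerbation in item 1 is severe or moderate-or-severe.

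Section 9.3.2.2 makes resource use a secondary endpoint, counted over follow-up, and lists "Mean monthly HCRU (including frequency of hospitalizations, ER visits, OP visits"). Section 9.7.1 says "We will also compare the mean monthly (to account for variable follow-up time) per patient HCRU", and gives the scope and period as "per patient HCRU (all-cause and asthma related hospitalizations, ER visits, and outpatient visits) during the follow-up period, between the two groups". It adds, for exacerbations, "We will report rates in patient-years to account for variable follow-up time", and it takes the 6-month and one-year measures in patients with at least that much follow-up. The abstract repeats this analysis. No section gives any of these endpoints a follow-up period of its own.

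Section 9.3.2.1 defines a severe exacerbation as an asthma-primary hospitalization or ER visit.

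**The concern.** Stopping at the first event suits a time-to-first-event model. It does not suit a count of resource use, because the event that closes the observation period is the main asthma resource-use event. What a first exacerbation leads to (readmission, repeat ER visits, aftercare) falls outside follow-up. Dividing by months is meant to handle unequal follow-up, but here the outcome itself sets the length of follow-up, so the division cannot do that job. Resource use is one of the two aims in the study title, and an analyst who programs section 9.1 as written would produce figures that do not describe it.

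**Working it through.** The documents give no event rate, persistence or HCRU figure, so there is no planned number to reproduce. Every rate and duration below is an assumption.

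**1. Definitions side by side.**
- Follow-up ends at the first exacerbation (9.1).
- A severe exacerbation is an asthma-primary hospitalization or ER visit (9.3.2.1).
- HCRU is counted within follow-up (9.3.2.2, 9.7.1).

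So the number of asthma-primary hospitalization/ER episodes per patient is 0 or 1. If 1, it falls on the last day. If the censor day were left out, the count would be 0 in both groups. Patients without an exacerbation are not affected by this rule.

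**2. One patient.** An ER visit on day 5 gives 1 / (5/30.4) = 6.1 visits per month. The same visit in a 6-month window gives 1/6 = 0.17 per month, about 36 times lower.

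**3. Why the per-patient mean inflates.** Take a low constant daily rate λ, a fixed time on treatment of C days, and a one-day minimum follow-up. The chance of an event is about λC. Given an event, its day is roughly uniform on (0, C), so the mean of 1/follow-up is (1 + ln C)/C. The product is λ(1 + ln C), against a true rate of λ. The inflation factor is therefore 1 + ln C:
- C = 90: 1 + 4.50 = 5.50
- C = 177: 1 + 5.18 = 6.18
- ratio of the two: 6.18/5.50 = 1.12, with identical true rates.

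The factor depends on the one-day minimum, a convention the plan does not state.

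**4. Simulation.** Inputs: 0.05 or 0.15 severe events per patient-year; gamma frailty variance 2 or 5; time on treatment 45 days plus an exponential time (mean 45 or 150), capped at 365, which averages about 90 or 177 days; 2,000,000 patients per scenario.

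| Quantity | Result |
|---|---|
| Per-patient monthly mean / truth | about 5 to 6 |
| Pooled events / person-months, relative to truth | 0.82 to 0.98 |
| Share of events lost (not first events) | about 2 to 21% |
| Per-patient mean, 177-day arm vs 90-day arm, equal true rates | about 10% higher |

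**5. Other inputs.** With median persistence of 6 months and frailty variance 0 to 2:
- At 0.2 events per year the true mean of 0.0167 per month becomes 0.096 to 0.100.
- Events lost are 3 to 9% at 0.05 per year, 12 to 26% at 0.2, and 21 to 39% at 0.4.
- If a moderate-or-severe event ends follow-up (0.5 to 1.0 per year, frailty variance 1), 36 to 51% of such events are lost.
- For outpatient visits (0.5 per month, plus 1.5 extra in the month after an exacerbation), a true 0.51 to 0.53 becomes 0.50.

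**6. Between groups.**
- A true proportional rate ratio of 0.80 is seen as 0.80 to 0.83.
- If one group has twice the recurrence after a first event, a true pooled ratio of 1.19 is seen as 1.00.

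**7. The 6- and 12-month measures.** A patient with an exacerbation before month 6 has less than 6 months of follow-up under section 9.1, and so is not in the 6-month subgroup. Everyone who is in it was event-free to that point. The rate and proportion up to month 6 are then close to zero, whatever the drugs do. The same holds at one year.

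**The case against.** **Item 1 may have been meant only for the time-to-first-event analyses.** The near-empty 6-month result suggests so. That is plausible, but no section says it, and the text as it stands applies the rule to every endpoint. At the least a clarification is needed.

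**A reader might infer that HCRU stops as soon as asthma resource use begins.** The documents do not support this. Asthma outpatient visits and all-cause use before the first exacerbation are counted. Asthma-related HCRU is not limited to primary-diagnosis claims, so the limit of one episode holds only for asthma-primary hospitalization/ER use.

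**A reader might also infer that the group comparison is wrong by 5 to 6 fold.** It is not. The inflation affects the level in each group and largely cancels in the ratio when persistence is similar and rates are proportional. It also requires averaging patient-level ratios with day-level denominators. The plan's wording points that way but does not rule out total visits over total months. The 10% artefact needs an assumed twofold gap in time on treatment. Even at 17,882 versus 35,764 patients (the section 9.5 count after COPD exclusion, matched 1:2) it is roughly half a standard error, so it alone is unlikely to drive a conclusion.

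These limits stand. They do not restore the lost repeat events and aftercare or the 6- and 12-month measures. Section 9.1 itself expects potentially large adherence differences between the groups, so similar persistence cannot be taken for granted.

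**Conclusion.** The point holds on the text: a stated rule, not a missing detail, closes HCRU observation at the first exacerbation. Two consequences follow from the definitions alone. There is at most one asthma-primary hospitalization/ER episode per patient, with nothing counted afterwards, and the 6- and 12-month measures are close to zero among patients followed that long.

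The numerical sizes rest on assumed rates, frailty, persistence and a one-day minimum: about 5 to 6 fold for averaged patient-level ratios, 0.82 to 0.98 of the truth for a pooled rate, and about 10% between groups with a twofold gap in time on treatment. A biased group ratio is possible but not established. What is established is that differences in recurrence or aftercare cannot be seen.

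HCRU is a secondary endpoint. Ending follow-up at the first severe exacerbation is right for the primary endpoint, which is unaffected provided item 1 means a severe event there. This should be fixed before analysis; it does not undermine the study's main comparison.

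**What to change.** In sections 9.1 and 9.7.1:

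- Restrict censoring event 1 to the two time-to-first-event endpoints, and state which exacerbation (severe, or moderate-or-severe) ends follow-up for each.
- For HCRU, rescue medication, the exacerbation rate and the 6- and 12-month proportions, end follow-up only at events 2 to 5: switch, discontinuation, end of enrollment, end of data.
- Count all qualifying events, including the one on the exacerbation date.
- Estimate group rates as total events over total person-time, not as the mean of patient-level ratios. A negative binomial model with a log person-time offset is one option.

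Two matters belong in the same edit. Section 9.1 also describes unexposed windows within follow-up, which fits poorly with ending follow-up at discontinuation; the two should be reconciled. And if an exacerbation prompts a switch, the use that follows is still lost, which should be listed as a limitation.

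The cost is protocol wording, one extra end date per patient and a little programming on the same claims. No new data are needed.

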Proprietary confidential information © 2021 Boehringer Ingelheim International GmbH or one or more of its affiliated companies for a patient with a prescription claim with 30 days supply on January 1st will be January 1st and February 15th respectively (30 days' supply +15 days). We will run sensitivity analyses on the exposure window using 0% and 100% additional days. These time varying exposure covariates will be included in the Cox PH regression.

If statistical differences are found after PSM, then the study team will make a determination to either include them as covariates in the regression analysis (Cox PH), or develop interaction terms to match on, or discontinue the study. In the event of study discontinuation, partial results (all analysis leading up to and including PSM) will be provided in a final report.

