9.5 STUDY SIZE

There are 25,291 patients with a prescription claim for tiotropium (1.25mcg, October 2015-May 2020) identified for analysis and 1,125,657 patients with ICS/LABA prescription claims (July 2014-May 2020). After excluding patients with COPD there are 17,882 patients in the Tio group and 921,804 patients in the ICS/LABA group. Further inclusion-exclusion criteria as well as restricting the Tio group to those with concurrent ICS monotherapy, will be applied to arrive at the final sample.

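### Rescue (SABA) use is compared as a plain proportion over follow-up that differs by patient, so unequal follow-up between arms would appear as a difference in rescue use

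*Combined protocol and SAP*

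**What the plan says.** Section 9.3.2.2 lists the endpoint: "Proportion of patients with use of rescue medications (defined as patients with one or more SABA claims during the follow-up period". It also lists "Proportions of patients with Health care resource utilization (HCRU", which is likewise a yes/no measure over follow-up.

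For the analysis of rescue use, Section 9.7.1 says "Proportions of patients with and without rescue medication use will be compared between the two groups as well", and the Abstract (Data analysis) says the same. Neither place names a horizon, a minimum follow-up, an offset, a censoring method or a model.

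Section 9.1 runs follow-up from the index date to a censor date, set by one of five events. The first three are "1. Date of first exacerbation, 2. Date of medication switch, 3. Discontinuation of medication", the last being the claim date plus days' supply plus 50%. The other two are end of enrollment and end of data.

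The same paragraph of Section 9.7.1 does take variable follow-up into account elsewhere. Exacerbation proportions are restricted to patients with at least 6 months or a year of follow-up, exacerbation rates are per patient-year, and HCRU frequency is per month.

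**The concern.** The chance of at least one claim rises with time observed. A proportion counted over unequal observation periods therefore mixes how often patients use rescue medication with how long they were watched.

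The plan's own wording makes unequal follow-up plausible. Section 9.1 sets out to "account for differences in inter-group adherence levels" and refers to "potentially large differences in medication adherence rates", and the same section lists discontinuation as a censoring event. Matching balances variables measured at baseline. It does not balance follow-up after index.

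Rescue use is a listed secondary endpoint, and a gap produced by follow-up alone could be read as a treatment effect. The proportion with any HCRU has the same weakness, but Section 9.7.1 writes no comparison of it, so it is affected only if it is compared. The primary endpoint, the exacerbation rates and mean monthly HCRU are not affected by this point.

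**Working it through.** The plan gives no SABA rate, follow-up length or sample size calculation for this endpoint, so there is no figure to reproduce. What follows shows only how the proportion behaves.

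**Assumptions.** Both arms have the same constant rate λ of first SABA claim: 0.5, 1 or 2 per year (365.25 days). Follow-up is a minimum of m days plus an exponential time, with the stated mean. The value m = 45 comes from the Section 9.1 example, in which a 30-day supply gives exposure dates of "January 1st and February 15th respectively" (30 + 15 = 45 days). Follow-up can end earlier for other reasons, so m = 0 is also shown.

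**Formula.** P(any claim) = 1 − exp(−λm) / [1 + λ(mean − m)].

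**Worked case, λ = 1 per year.**
- m = 0, mean 120 days: 1 − 1/(1 + 120/365.25) = 24.7%. Means of 150 and 200 days give 29.1% and 35.4%.
- m = 45, mean 120 days: exp(−45/365.25) = 0.884, and 1 − 0.884/(1 + 75/365.25) = 26.7%. Means of 150 and 200 days give 31.3% and 37.9%.

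**False difference in percentage points, true use identical.**

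| λ per year | m (days) | 120 vs 120 | 120 vs 125 | 120 vs 150 | 120 vs 200 |
|---|---|---|---|---|---|
| 0.5 | 0 | 0 | 0.5 | 2.9 | 7.4 |
| 1 | 0 | 0 | 0.8 | 4.4 | 10.7 |
| 2 | 0 | 0 | 1.0 | 5.4 | 12.6 |
| 0.5 | 45 | 0 | 0.5 | 3.1 | 7.7 |
| 1 | 45 | 0 | 0.8 | 4.7 | 11.3 |
| 2 | 45 | 0 | 1.1 | 5.8 | 13.1 |

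**Does a time-aware estimate remove it?** This was simulated with λ = 1 per year, m = 45, means of 120 versus 200 days, a 6-month horizon (182.6 days) and 1,000,000 patients per arm.
- Censoring independent of use: Kaplan-Meier gives 39.3% versus 39.4%. The true value is 1 − exp(−0.5) = 39.3%. The crude gap is 11.3 points.
- Heavier users stop sooner, modelled as a shared gamma frailty with variance 0.25, 0.5 and 1 on both the SABA rate and the stopping rate: Kaplan-Meier leaves about 1.8, 2.5 and 2.9 points, against about 11 crude.
- The same, with stopping rates reset so that mean follow-up stays at 120 versus 200 days (400,000 per arm): Kaplan-Meier leaves about 2.2, 3.5 and 4.5 points, against 9.6, 8.1 and 5.2 crude. At variance 1 it reads about 19% and 23% where the truth is about 33%.
- Fixed 6-month window from index, ignoring discontinuation, with independent end of enrollment (assumed mean 3 years): 33.3% versus 33.4% at variance 1, true value 33.3%. This assumes that stopping treatment does not change SABA use.

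**The case against.** **Persistence may not drive follow-up.** Section 9.1 ends follow-up at discontinuation, but also defines non-exposure windows within follow-up by the same rule of days' supply plus 50%. Section 9.7.1 then models changes in exposure over follow-up. If discontinuation always ended follow-up, little unexposed time would remain to model. If it does not, follow-up depends mainly on enrollment, data end, switch and exacerbation. Index year and insurance type are matching variables, which makes a large gap less likely. This stands as a reason for doubt about size. It does not supply the missing horizon, and the two statements need reconciling.

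**The text does not say the comparison is unadjusted.** The Abstract says exposure will be recorded with time-varying covariates for all endpoints. That is fair as far as it goes: the plan is underspecified and does not commit to a crude test. But no regression is named for this endpoint, so the covariates have nothing to act on.

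**The other endpoints are not a clean benchmark.** Restricting to patients with at least 6 or 12 months of follow-up, when follow-up ends at first exacerbation, would read literally as dropping early exacerbators. This stands, and that device should not be copied for rescue use.

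**Stronger readings the documents do not support.** A reader might infer that the Tio arm will have the shorter follow-up because two products must be kept up, given "restricting the Tio group to those with concurrent ICS monotherapy" in Section 9.5. That passage describes sample selection, and no rule says that the end of one product ends follow-up. A reader might also infer that the bias favours a particular arm, or that it reaches mean monthly HCRU. No follow-up lengths or direction are given, and monthly HCRU is already scaled for time.

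**Conclusion.** The point holds as a conditional one. As written, the rescue-use comparison has no horizon and no person-time adjustment, so any difference in follow-up between arms passes into the result. With equal follow-up the artefact is zero. Under the assumed equal rates of 0.5 to 2 per year it is 2.9 to 5.8 points at mean 120 versus 150 days and 7.4 to 13.1 points at 120 versus 200 days. These figures rest on constant rates, the assumed shape of follow-up and durations the documents do not give, so the true size and direction are unknown.

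A reader might conclude that Kaplan-Meier alone settles the matter. It does so only if censoring is independent of use. Under strong dependence it removes little of the gap and understates both arms, so a second estimate is needed beside it. Because this is a secondary endpoint and the primary is untouched, the change should be made before analysis, but the study does not depend on it.

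**What to change.** 1. Replace the plain proportion with the Kaplan-Meier cumulative incidence of first SABA claim at 6 months in all matched patients, with numbers at risk. State that it assumes censoring independent of use.
2. Report beside it SABA use over a fixed 6 months from index, regardless of discontinuation or switch, censored only at end of enrollment or end of data.
3. State that follow-up for SABA use does not end at the first exacerbation.
4. Report follow-up length and reason for ending by arm. Reconcile censoring at discontinuation with the non-exposure windows in Section 9.1, and say whether the end of one Tio-arm product ends follow-up.
5. Apply the same to the proportion with any HCRU, if it is compared.

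The cost is protocol wording and slightly more analysis, with no new data. Few patients may remain at risk. In the case of 1 claim per year, m = 45 and 120 versus 200 days, the share still claim-free and followed at 6 months is exp(−0.5) × exp(−137.6/75) = 9.7% versus exp(−0.5) × exp(−137.6/155) = 25.0%. At 12 months it is 0.5% versus 4.7%. The fixed window also answers a different question: use after starting treatment, not use while on it.
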